## Protocol Synopsis

PROSPECTIVE ASSESSMENT OF PVC SUPPRESSION IN CARDIOMYOPATHY (PAPS): A Pilot Study	
Part I - PAPS pilot randomized trial	
Study / Objectives	Assess the feasibility of enrolling, randomizing treatment strategies and retaining participants with frequent PVCs and associated CM.
Interventions	3-month observation period followed by either radiofrequency ablation (RFA) or antiarrhythmic drugs (AADs). All interventions (RFA and all proposed medications) are FDA approved and are currently standard of care for subjects with frequent PVCs.
Study Design	Multicenter randomized prospective study
Eligible subjects	Subjects with frequent PVCs (equal to or greater than 10% burden) and cardiomyopathy with calculated left ventricular ejection fraction (LVEF) ≤ 45%.
Planned number of subjects	This study will enroll between 36-39 subjects – 3 subjects per center (enrollment completed within 18 months).
Number of participating sites/ countries	At least 12 centers in the United States and one in Canada
Primary Endpoint(s)	
 
1. Improvement of LVEF after PVC suppression at 12-month follow-up. This is chosen as the primary-endpoint due to the known prognostic value of LVEF. The lower the LVEF, the higher the risk of sudden cardiac death and heart failure. This will compare the overall improvement or change in LVEF between RFA and AAD groups. This end-point will support that either RFA or AADs have an overall better outcome due to significant improvement of LV function with potential impact on morbidity and mortality associated with PVC-CM.
 
2. Responders to PVC suppression strategy at 12-month follow-up. Assessment of the number of responders (delta LVEF ≥ 10%) after PVC suppression strategies (RFA or AADs) will assess the effectiveness of RFA and AADs to reverse or improve cardiomyopathy induced by frequent PVCs. Evidence that either RFA or AADs is superior to improve or even reverse LV dysfunction in subjects with high burden PVCs could have significant impact of morbidity and mortality including future heart failure and ventricular arrhythmias, and also may avoid ICD implantation.
 

Additional Endpoint(s)	
 
1. Efficacy of RFA vs AADs groups to achieve successful PVC suppression at 12-month follow-up, defined as a reduction of PVC burden ≥80% (regardless of LVEF change). Understanding the success rate of PVC suppression between RFA and AADs will help better determine the best treatment to those subjects with high PVC burden.
 
2. Composite end-point of adverse events at 12-month follow-up, including worsening in NYHA functional class (I-IV), number of HF and cardiac-related admissions, RFA complications and AAD adverse effects and cardiovascular death.
 
3. Composite end-point of arrhythmia burden at 12-month follow-up, including PVC recurrence, non-sustained (< 30sec) and sustained (> 30sec) ventricular arrhythmias and arrhythmic sudden cardiac death.
 

Follow up Schedule
	
Subjects will be screened via chart review. If the inclusion criteria is met, subject will be asked to participate in the study during Visit 1 (Week 0)  Each enrolled subject will be followed at the following visits:
 
 
- Week 0 –, Enrollment, informed consent and clinical evaluation
 
- Week 9 – ECG and ambulatory ECG recording
 
- Week 12 – Clinical evaluation and echocardiogram
 
- Week 12-15 – Initiation of intervention (RFA or AADs)
 
- Week 21 – Clinical evaluation
 
- Every 3 months after RFA or AADs (week 38, 50 and 64) – Clinical assessment with occasional testing (echocardiogram and ambulatory ECG recording)
 
- Week 64 – Complete protocol.
 
 
All visits and testing are clinically indicated and considered standard of care. Most of these subjects receive this follow up regardless of participation in the study.

Study Duration
	
Study duration is approximately 36 months.  Each subject will be followed for at least 15 months, which includes a 3-month observation period and 12months after intervention is initiated.
 
 
- Enrollment and subject follow up of all subjects is estimated to be completed within 3 years.
 


Key Inclusion Criteria
	
 
- LV dysfunction (calculated LVEF <math>\leq</math>45% based on Echo) within 150 days of Enrollment (Day 0)
 
- Average PVC burden <math>\geq</math> 10 % by at least a 24-hr ambulatory ECG monitor (within 150 days of Enrollment (Day 0)
 

Key Exclusion Criteria	
 
- Age < 18 years old
 
- Current amiodarone use or within last 2 months
 
- Current use of any antiarrhythmic drug class I or III
 
- Contraindication to use amiodarone or any other class III antiarrhythmic
 
- Severely symptomatic PVCs (defined as incapacitating palpitations or pre-syncope) and unable to complete a 3-month observation period
 
- Severe/ significant CAD with planned revascularization in the near future
 
- Complete AV block and pacemaker dependent
 
- Pacemaker or ICD with > 10% of right ventricular pacing
 
- Severe valvular heart disease or planned valvular/cardiac surgery
 
- Uncontrolled or untreated endocrinopathies
 
- Uncontrolled HTN systolic (BP > 180mmHg or diastolic >110 mmHg)
 
- Hypertrophic cardiomyopathy
 
- Systemic infiltrative and immune disorders
 
- Family history of dilated CM in a first degree relative
 
- Alcohol abuse or illicit drug use
 
- Contraindication to short-term acute anticoagulation (due to possible randomization to RFA)
 
- Atrial fibrillation and flutter with Rapid VR with possible tachycardia-induced cardiomyopathy
 
- Pregnant or lactating women
 
- Possible infectious etiology of cardiomyopathy
 
- Previous PVC ablation
 

Statistical Methods	
Primary hypothesis	
1) A large-scale randomized PAPS clinical study is feasible with minimal barriers of enrollment, treatment crossover and drop out due to a unique design including a short observation period and PVC suppression strategy in all participants.
 
2) The rate of responders (defined as improvement of LVEF <math>\geq</math> 10% points) with HF medical therapy alone during observation period will be less than 15% in subjects with CM associated with frequent PVCs. In contrast to HF medical therapy alone, RFA and AADs will have a responder rate of at least 35% in the same population. Furthermore, RFA will have a greater 1-year response rate when compared to AAD therapy.
 
3) RFA will have a lower rate of composite adverse events (worsening NYHA class, HF admission, treatment side effects & complications, and death), arrhythmia burden and a better long-term tolerance than AADs.

Sample Size	
This has been estimated solely on primary end-point of improvement in LV ejection fraction between PVC suppression strategies (RFA vs. AADs groups). Assuming that subjects would have a LVEF level of 25% (SD=5%) in each of the groups at baseline and LVEF levels of 40% and 35% (SD=10%) in the RFA and AAD groups at 12 months, respectively. A within subject correlation of 0.25 was assumed along with an inter-site standard-deviation of 1%. This model was fit assuming that, on average, 10% of the subjects would drop out randomly. Approximately 140 total subjects (70 per group) should be enrolled to reject the null hypothesis that the mean LVEF between RFA and AAD groups are equal with probability (power) 0.8 and Type I error probability of 0.05. As a pilot study we have determined to enroll at least 20% (30 subjects) of preliminary sample size estimation to understand feasibility and key aspects of subject enrollment, randomization and retention to properly power a large-scale randomized PAPS study. Sample size is increased

	by 15% (6 additional subjects, between 36-39 subjects total – 19 to 20 subjects in each treatment group) to take into account possible spontaneous improvement of LV dysfunction during 3-month observation period between treatment strategies.
Part II - Prevalence of PVC- Cardiomyopathy in the overall ambulatory Holter population	
Study / Objectives	Estimate the prevalence of cardiomyopathy (CM, LVEF $\leq$ 45%) and frequent premature ventricular contractions (PVCs $\geq$ 10%) in the overall population receiving ambulatory ECG Holter monitors.
Primary hypothesis	The prevalence of CM (LVEF $\leq$ 45%) and frequent PVCs ( $\geq$ 10% burden) is largely under recognized in subjects undergoing ambulatory ECG Holters.
Study Design and duration	Multicenter prospective and retrospective population-based database of all subjects undergoing ambulatory ECG monitor during 24-month period.
Eligible subjects	All-comers undergoing at least a 24-hr ambulatory ECG monitor for any clinical indication
Planned number of subjects	A total of 20,000 ambulatory ECG monitors – 1,500 subjects per center (to be completed within 24 months).
Planned number of participating sites/ countries	At least 12 centers in the United States and one in Canada

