**Definitions:**

The *diagnosis criteria for PVC-CM* is based on LVEF  $\leq$  45% (by echocardiography) and average PVC burden  $\geq$  10% in an ambulatory ECG Holter monitor that meet the inclusion and exclusion criteria (Table 1), regardless of severity and time of onset. LVEF and PVC burden must be within 150 days of Enrollment Visit (Day 0).

*Responders are defined as an LVEF increase greater than 10% points regardless of intervention.*

If screening confirms eligibility (LVEF  $\leq$ 45% and PVC burden  $\geq$  10%), a baseline visit will be scheduled to obtain subject's demographics and medical history, 12-lead ECG, Minnesota living with HF quality of life (QOL) questionnaire, NYHA functional class and cardiac magnetic resonance (CMR) if clinically indicated. Subjects that refuse enrollment, will be asked to participate in a PVC-CM registry to follow their response and crossover to different treatment strategies.

If subjects meet inclusion criteria (Table 1) during screening, informed consent should be obtained. Stratified randomization to either RFA or AADs will be performed at the time of enrollment (baseline visit, week 0). Based on our preliminary data, we expect that around 30% of subjects will have a PVC burden  $>$ 20%. Thus, a *stratified randomization based PVC burden (assessed by Holter) above and below 20% is needed to assure that subjects in both groups (RFA vs. AAD) are equally distributed between PVC burden above and below 20%.* Stratified randomization will be performed using approved software available at the Coordinating Center only.

If a subject is randomized to the RFA arm, a RFA procedure (Visit 1) should be scheduled at the time of randomization due to usual 8-week next available RFA appointment in most participating centers. Yet both, RFA and AAD interventions should only occur or be initiated after completion of a 3-month observation (Table 2 - Visit Tx-V1, week 12-15).

A 3-month observation period will assess spontaneous variation of PVC burden and improvement or deterioration of LV function. During the final 3-month observation visit (Week 12), LVEF and Holter will be repeated to confirm eligibility if PVC burden and LVEF remains  $\geq$ 10% and  $\leq$ 45%, respectively.

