### Exclusion Criteria

1. Age < 18 years old
2. Current Amiodarone use or within last 2 months
3. Current use of any antiarrhythmic drugs class I or III
4. Contraindication to use amiodarone or any other class III antiarrhythmic
5. Severely symptomatic PVCs (defined as incapacitating palpitations or pre-syncope) unable to complete a 3-month observation period
6. Severe/significant CAD with planned revascularization in the near future
7. Complete AV block and pacemaker dependent
8. Pacemaker or ICD with > 10% of right ventricular pacing
9. Severe valvular heart disease or planned valvular/cardiac surgery
10. Uncontrolled or untreated endocrinopathies
11. Uncontrolled HTN (systolic >180 mmHg or diastolic > 110 mmHg)
12. Hypertrophic cardiomyopathy
13. Systemic infiltrative and immune disorders
14. Family history of dilated CM in a first-degree relative
15. Alcohol abuse or illicit drug use
16. Contraindication to short-term anticoagulation (due to possible randomization to RFA)
17. Atrial fibrillation and flutter with Rapid VR with possible tachycardia-induced cardiomyopathy
18. Pregnant or lactating women
19. Possible infectious etiology of cardiomyopathy
20. Previous PVC ablation

*If both PVC and/or LVEF criteria are not met after the observation period, the subject will be withdrawn from the study and treatment will be as recommended by primary provider. We will ask the subject to participate in a PVC-CM registry with assessment of PVC burden and LVEF as clinically indicated during the following 12-month study. When allowed by the IRB, informed consent will include an option for participation in this registry as a contingency in case subjects no longer meet criteria or decide to withdraw participation. These subjects will continue treatment as recommended by their local clinical electrophysiologist.*

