## **B. Scheduled Visits**

When a subject is first identified during a visit or when reviewing a 24-48 hour or 2-week ambulatory ECG monitor (Zio Patch), we request that sites briefly screen the subject by reviewing the inclusion/exclusion criteria of the protocol. Assessment of calculated LVEF (obtained by transthoracic echocardiogram) and PVC burden is acceptable as long as it has been obtained within the prior 150 days. If the subject meets both, then the subject should be scheduled for a Baseline Visit (Observation – Visit 1).

Subjects enrolled in the study will have visits as outlined in Table 2 and Figure 1. There are some circumstances where the screening and Observation Visit 1 may occur the same day.

*i. Observation – Visit 1.* After inclusion/exclusion criteria is confirmed, the study protocol will be explained to the subject and informed consent should be obtained. If the subject agrees to participate, the following data should be collected using appropriate forms (see Data collection forms), including general info and demographics, current medical therapy, physical exam, NYHA functional class and Minnesota HF quality of life questionnaire (QOL). Physical examination and NYHA functional class can be completed

based on a prior visit (up to 120 days prior). A 12-lead electrocardiogram and cardiac MR should be requested if clinically indicated. Alternatively, we will request that sites provide images of prior ECG or CMR if performed within the prior 120 days. Sites should obtain a copy of the transthoracic echo (during screening Visit) and mail it to the Echo Core laboratory led by [name] III, M.D. The Echo report should be uploaded to REDCap. Finally, a 2-week Zio Patch (IRhythm ambulatory ECG device) should be placed on the subject to obtain a long-term PVC burden. The subject will mail the device to IRhythm for analysis. Instructions will be provided to all centers on the placement of this device.

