#### *Rate of spontaneous recovery of CM and PVCs suppression during the 3-month observation period and assess the recurrence of CM and PVCs during a 12-month follow up.*

Due to a known temporal variability of PVC burden over time, it is unclear how often spontaneous variability of PVCs would lead to observing what appears to be spontaneous resolution of PVCs (e.g., without any intervention), which could in theory result in spontaneous improvement of LV dysfunction if CM is secondary to frequent PVCs.

We will assess and compare the PVC burden and LVEF between the time of enrollment and at the end of the 3-month observation period. *This pilot study will allow us to understand the degree and rate of spontaneous improvement of LVEF and reduction of PVCs (control phase) to properly power a large multicenter PAPS study.* Subjects that do not meet both inclusion criteria (LVEF  $\leq 45\%$  and PVC burden  $\geq 10\%$ ) at the end of the observation period will be considered a screen failure, and will be included in a PVC-CM registry if consent has been provided. Based on preliminary data, we believe that less than 10% of subjects will have spontaneous improvement of LVEF  $> 45\%$  and PVC  $< 10\%$ . Registry subjects will have PVC and LVEF assessment every 6 months for the remaining 12 months to understand the recurrence of CM and PVCs (see Section A.1).

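### Antiarrhythmic exclusion is judged only at enrolment while the enrolment echo may be 150 days old, so in some subjects the observation-phase LVEF change can include the effect of stopping a drug

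*Combined protocol and SAP*

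**What the plan says.** **Drug status.** The Protocol Synopsis excludes "Current amiodarone use or within last 2 months" and "Current use of any antiarrhythmic drug class I or III". Table 1 has the same two rules as exclusion criteria 2 and 3, the second reading "Current use of any antiarrhythmic drugs class I or III". Both are judged at enrolment.

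**Qualifying tests.** Under Definitions (Study Design Part I, Section A), "LVEF and PVC burden must be within 150 days of Enrollment Visit (Day 0"). Section B repeats that "PVC burden is acceptable as long as it has been obtained within the prior 150 days", and covers the calculated LVEF in the same sentence. A date is the only condition tied to when these tests were done. In Table 2 the echo at the first observation visit carries the 150-day footnote, and Section B has sites send the screening echo to the core laboratory. No new echo is required at Week 0. The next required echo is at Week 12.

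**Use of the change.** Section F states: "We will assess and compare the PVC burden and LVEF between the time of enrollment and at the end of the 3-month observation period". It treats this change as spontaneous, calls the period the control phase, and intends the result to help power the large trial. The second hypothesis in Specific Aims puts the responder rate on heart failure therapy alone during observation below 15%.

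**Stratification.** Definitions states that "stratified randomization based PVC burden (assessed by Holter) above and below 20% is needed". Randomisation is at Week 0, the visit at which the first two-week Zio Patch is only being placed.

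**The concern.** The exclusion rules are there so that subjects enter off antiarrhythmic drugs, but they are tested on one date and the enrolment LVEF can come from another. A subject may have the echo on drug, stop the drug, satisfy criteria 2 and 3 on Day 0, and have the second echo off drug at Week 12. The difference between the echoes then mixes natural course and heart failure therapy with withdrawal of an antiarrhythmic.

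Estimating the observation-phase rate is one of the pilot's stated purposes, and that rate carries forward into the design of the full trial. Historical tests should be common: Section L expects most subjects to be found through Part II, which also collects Holters retrospectively. Prior drug exposure is plausible. In the survey reported under Significance, 12% to 18.8% of electrophysiologists chose antiarrhythmic drugs across the scenarios described. That is not the share of enrolled subjects who recently stopped one, which the documents do not give.

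**Working it through.** **1. The plan's sample size.** Inputs from Section I: 12-month difference 40 − 35 = 5 points, SD 10, power 0.80, alpha 0.05 (taken as two-sided), 10% dropout.
- n per arm = 2 × (1.96 + 0.84)² × 10² / 5² = 62.7, rounded up to 63.
- 63 / 0.9 = 70 per arm, 140 in total. This reproduces the stated figure.
- No observation-phase rate enters this calculation, so the point does not change 140. It concerns a rate the pilot is meant to supply for later planning.

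**2. Exposed part of the look-back.**
- Amiodarone, reading 2 months as 60 days: 150 − 60 = 90 days, and 90/150 = 60%. Reading it as 59 to 62 days gives 91 to 88 days.
- Other class I or III drugs: no look-back, so essentially all 150 days.
- An echo can also fall inside the plan's own 2-month window without being on drug. With amiodarone stopped on Day −61, an echo on Day −30 is 61 − 30 = 31 days after the stop, yet criterion 2 is met on Day 0.

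**3. Drug status at Week 12.** The visit window opens on Day 84. Assuming no class I or III drug is started during observation, a subject is then at least about 60 + 84 = 144 days off amiodarone, or at least 84 days off another agent.

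**4. Effect of one subject on the observation-phase rate.**
- If responder status flips: 1/39 = 2.6 points to 1/36 = 2.8 points. Two flips: 5.1 to 5.6 points.
- If status does not flip: zero.

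**5. Illustration.** The documents give neither the share affected nor the size of a withdrawal effect, so both are assumed. Take an SD of 3-month LVEF change of 10 points and a true responder rate of 15%. The mean change is then 10 − 10 × 1.036 = −0.36. If withdrawal shifts LVEF by d, an affected subject responds with probability 1 − Φ((10.36 − d)/10), which is 0.485 for d = +10 and 0.021 for d = −10. With share f affected, the observed rate is (1 − f) × 0.15 + f × that probability.

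| Share affected | d = −10 | d = −5 | d = +5 | d = +10 |
|---|---|---|---|---|
| 10% | 13.7% | 14.1% | 16.5% | 18.4% |
| 30% | 11.1% | 12.4% | 19.4% | 25.1% |

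The bias in mean change is f × d: ±1 point at a 10% share and ±3 points at 30%, for d = ±10. The expected movement per affected subject at d = +10 is (0.485 − 0.15)/39 = 0.9 points to (0.485 − 0.15)/36 = 0.9 points, so under 2 points for two subjects.

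**6. Sampling error for scale.** The 95% half-width at 15% is 1.96 × √(0.15 × 0.85/n): 11.7 points at n = 36 and 11.2 points at n = 39.

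**The case against.** **Readings a reader might infer, which the documents do not support**
- *The treatment-phase result rests on an on-drug baseline.* A new echo is done at Week 12, eligibility is confirmed again on it, Section B calls the first treatment visit the baseline visit, and Section F takes the end of observation as the own-control reference. This protection depends on baseline meaning Week 12. The formula in Section F names no visit, and Table 2 labels both the first observation and the first treatment visit as baseline.
- *RFA versus AAD is biased through the stratum.* The 20% stratum can come from an on-drug Holter, but any misclassification precedes allocation and applies to both arms alike. It only makes the stratification less exact.
- *PVC change over observation is equally contaminated.* Zio Patches at Weeks 0 and 9 both follow drug stop, so this comparison can be made largely off drug.
- *60% of subjects are affected, or every affected subject moves the rate by 2.6 to 2.8 points.* The first figure is a share of calendar days, and the second requires a change of responder status.
- *The figure of under 10% in Section F is at risk by the same amount.* It describes a state at the end of observation (LVEF above 45% and PVC burden below 10%). It is not a change from enrolment, so it is a poor yardstick here.

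**What else can be said against the point.** No affected subject is shown. Titration of heart failure drugs during observation may move LVEF in every subject, and sampling error is large. Section H describes limited funds and reliance on clinically indicated imaging, which tells against compulsory repeat tests. All of this stands as a limit on size. It does not remove the point: titration is part of the heart failure therapy whose response is being estimated, whereas antiarrhythmic withdrawal is not. A wide interval does not correct a bias in a planning estimate. Medical history and current medication are collected, but no stop date has to be matched to the test dates, so affected subjects may not be identifiable afterwards.

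**Conclusion.** The point holds for one quantity: the observation-phase LVEF change, and the responder and spontaneous-improvement rates taken from it. The date gap follows directly from the text. Its effect cannot be sized from the documents, because the number of recently withdrawn subjects and the direction and size of any withdrawal effect are not given. Under the assumptions in the illustration, a 10% share moves a 15% rate to between 13.7% and 18.4%, and a 30% share to between 11.1% and 25.1%. The smaller case is well inside sampling error; the larger could blur the below-15% hypothesis.

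The treatment-phase LVEF change (if baseline is Week 12), the observation-phase PVC change and the RFA versus AAD comparison are largely unaffected. This is a cheap improvement to a planning estimate and not a threat to the randomised comparison.

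**What to change.** 1. Add to the CRF the stop date of amiodarone or any other class I or III drug, recorded against the dates of the qualifying echo and Holter.
2. State in Sections F and I that the observation-phase LVEF responder and spontaneous-improvement rates will be calculated without subjects whose enrolment echo was recorded on drug or within the plan's own exclusion window. Report the all-subject rates alongside, with the number left out.
3. Ask the investigators to reconcile the 150-day look-back with exclusion criteria 2 and 3. How they do so is a clinical decision for them.

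The cost is one CRF date and a few subjects fewer in one estimate. No repeat echo or Holter is needed, which respects the budget limits in Section H, and the sample size does not change.
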